10.13 Visit 7 (Month 6 ± 14 days)

1. Perform and record RSSQ prior to any other study procedures
2. Review and record interval history
3. Review and record any changes to concomitant medications
4. Record any AEs that occurred since Visit 6
5. Measure and record weight without shoes
6. Perform and record vital signs, including a blood pressure after the subject has been seated for 5 minutes
7. Perform and record oximetry
8. Perform abbreviated physical examination
9. Collect blood for clinical laboratory tests (comprehensive chemistry panel, ESR, hs-CRP, complete blood count with differential, direct bilirubin and LDH)
10. Collect urine for clinical laboratory test (urinalysis)
11. Administer 3 puffs of albuterol 15 minutes prior to spirometry if subject is likely to require induction to obtain sputum during the visit
12. Perform and record spirometry
13. Schedule Subject for ***Telephone Call 4***
14. Record any AEs that may have occurred during the study visit

10.14 Telephone Call 4 (Month 12 ± 1)

1. Review and record interval history since Visit 7
2. Record any AEs that occurred since Visit 7

10.15 Acute Illness/Early Termination Visit

1. Review and record RSSQ prior to any other study procedures
2. If Acute Illness or Early Termination Visit occurs before Visit 5, administer and review CFRSD prior to any other study procedures and record any AEs that occurred since last Visit or Telephone call
3. Review and record interval history
4. Review and record any changes to concomitant medications
5. Measure and record weight without shoes
6. Perform and record vital signs, including a blood pressure after the subject has been seated for 5 minutes
7. Perform and record oximetry
8. Perform a complete physical examination
9. Collect blood for clinical laboratory tests (comprehensive chemistry panel, ESR, hs-CRP, complete blood count with differential, direct bilirubin and LDH)
10. Collect urine for clinical laboratory test (urinalysis)
11. Collect urine for pregnancy test
12. Administer 3 puffs of albuterol 15 minutes prior to spirometry if subject performed a sputum induction during the study
13. Perform and record spirometry
14. Record any AEs that may have occurred during the study visit

For Healthy Volunteer Subjects:**10.16 Visit 1 (Screening Visit: Day -30 to -7)**

1. Review the study with the subject and obtain written informed consent and HIPAA authorization
2. Assign the subject a unique screening number
3. Record demographics and other baseline data
4. Record medical and surgical history
5. Record concomitant medications
6. Review inclusion/exclusion criteria
7. Perform and record vital signs, including a blood pressure after the subject has been seated for 5 minutes
8. Complete Donor History Questionnaire (DHQ)

9. Collect 32 ml blood for laboratory tests (infectious disease markers, CMV, CF mutations). Collect 2 ml blood for serum pregnancy test if applicable.
10. Record any AEs that may have occurred during the study visit from the time of consent

10.17 Visit 2 (Bone Marrow Aspiration)

1. Perform and record vital signs, including a blood pressure after the subject has been seated for 5 minutes
2. Review and record interval history
3. Review and record any changes to concomitant medications
4. Perform urine pregnancy test if applicable
5. Perform an abbreviated physical exam
6. Review inclusion/exclusion criteria
7. Perform bone marrow aspiration
8. Subject to rest for 30 minutes post-procedure
9. Record any AEs that may have occurred during the study visit

10.18 Follow-up Phone Call (24 (\pm 12) hours after Bone Marrow Aspiration)

1. Review and record interval history
2. Review and record any changes to concomitant medications
3. Record any AEs that may have occurred since bone marrow aspiration

11 ADVERSE EXPERIENCE REPORTING AND DOCUMENTATION

11.1 Adverse Events

An AE is any untoward medical occurrence in a clinical investigation of a patient administered a pharmaceutical product and that does not necessarily have a causal relationship with the treatment that occurs from the time of consent through Telephone Call 4 (Month 12 \pm 1). An AE is therefore any unfavorable and unintended sign (including an abnormal laboratory finding), symptom or disease temporally associated with the administration of an investigational product, whether or not related to that investigational product. An unexpected AE is one of a type not identified in nature, severity, or frequency in the current Investigator's Brochure or of greater severity or frequency than expected based on the information in the Investigator's Brochure.

The Investigator or Research Coordinator will probe, via discussion with the subject, for the occurrence of AEs during each subject visit and record the information in the site's source documents. AEs will be recorded in the subject CRF. AEs will be described by duration (start and stop dates and times), severity, outcome, treatment and relation to investigational product, or if unrelated, the cause.

AE Severity

The NCI's CTCAE Version 4.0, summarized in Table 2 below, should be used to assess and grade AE severity, including laboratory abnormalities judged to be clinically significant. It should be pointed out that the term "severe" is a measure of intensity and that a severe AE is not necessarily serious.

Table 2. AE Severity Grading (based on NCI's CTCAE Version 4.0)

Severity (Toxicity Grade)	Description
Grade 1	Mild; asymptomatic or mild symptoms; clinical or diagnostic observations only; intervention not indicated.
Grade 2	Moderate; minimal, local or noninvasive intervention indicated; limiting age-appropriate instrumental ADL*.
Grade 3	Severe or medically significant but not immediately life-threatening; hospitalization or prolongation of hospitalization indicated; disabling; limiting self care ADL**.
Grade 4	Life-threatening consequences; urgent intervention indicated.
Grade 5	Death related to AE.

A Semi-colon indicates 'or' within the description of the grade.

Activities of Daily Living (ADL)

*Instrumental ADL refer to preparing meals, shopping for groceries or clothes, using the telephone, managing money, etc.

**Self care ADL refer to bathing, dressing and undressing, feeding self, using the toilet, taking medications, and not bedridden.

AE Relationship to Investigational Product

The relationship of an AE to the study drug should be assessed using the following the guidelines in Table 3.

Table 3. AE Relationship to Investigational Product

Relationship to Drug	Comment
Definitely	Previously known toxicity of agent; or an event that follows a reasonable temporal sequence from administration of the drug; that follows a known or expected response pattern to the suspected drug; that is confirmed by stopping or reducing the dosage of the drug; and that is not explained by any other reasonable hypothesis.

Relationship to Drug	Comment
Probably	An event that follows a reasonable temporal sequence from administration of the drug; that follows a known or expected response pattern to the suspected drug; that is confirmed by stopping or reducing the dosage of the drug; and that is unlikely to be explained by the known characteristics of the subject's clinical state or by other interventions.
Possibly	An event that follows a reasonable temporal sequence from administration of the drug; that follows a known or expected response pattern to that suspected drug; but that could readily have been produced by a number of other factors.
Unrelated	An event that can be determined with certainty to have no relationship to the investigational product.

11.2 Serious Adverse Events (SAE)

An SAE is defined as any AE occurring at any dose that results in any of the following outcomes:

- death
- a life-threatening adverse experience
- inpatient hospitalization or prolongation of existing hospitalization
- a persistent or significant disability/incapacity
- a congenital anomaly/birth defect

Other important medical events may also be considered an SAE when, based on appropriate medical judgment, they jeopardize the subject or require intervention to prevent one of the outcomes listed.

11.2.1 Serious Adverse Experience Reporting

All SAEs will be documented (whether or not related to investigational product) on a SAE Report Form. The collection period for all SAEs will begin after informed consent is obtained and end at Telephone Call 4 (Month 12 ±1).

All SAEs will be reviewed by the site investigator and sent to the TDNCC, within one business day of the site learning of the event. The site will scan and email or fax the SAE report to:

Email address: [contact]

Direct dial [contact]

Study staff will notify the TDNCC of additional information or follow-up to an initial SAE Report as soon as relevant information is available. Follow-up information is reported on an SAE Report Form.

In accordance with the standard operating procedures and policies of the local IRB, the site investigator will report SAEs to the IRB. SAEs will be reported to the FDA in accordance with 21 CFR 312.32.

12 DISCONTINUATION AND REPLACEMENT OF SUBJECTS

12.1 Withdrawal of Subjects and Drop-outs

A subject may be discontinued from the study at any time if the subject, the investigator feels that it is not in the subject's best interest to continue. The following is a list of possible reasons for study or treatment discontinuation:

- Subject withdrawal of consent
- Subject is not compliant with study procedures
- Adverse event
- Lost to follow-up
- Physician request for early termination of study

If a subject experiences an AE, the subject will be followed and treated by the Investigator or the subject's physician until the abnormal parameter or symptom has resolved or stabilized. Subjects will be encouraged to complete an Early Termination Visit.

All subjects are free to withdraw from participation at any time, for any reason, specified or unspecified, and without prejudice. If the subject withdraws from the study and also withdraws consent for disclosure of future information, no further evaluations should be performed, and no additional data should be collected. The Investigator may retain and continue to use any data collected before such withdrawal of consent. Any samples already being analyzed will be completed and any stored samples will be destroyed if still linkable.

Reasonable attempts will be made by the investigator to provide a reason for subject withdrawals. The reason for the subject's withdrawal from the study will be specified in the subject's source documents. Subjects who withdraw from the study will be replaced if they withdraw before Visit 5. Refer to Section 10 for early termination procedures. If a subject withdraws on the day of hMSC infusion, then the Early Termination Visit will be performed on Day 4-9.

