13 PROTOCOL VIOLATIONS

A protocol violation occurs when the subject or investigator, fails to adhere to significant protocol requirements affecting the inclusion, exclusion, subject safety and primary endpoint criteria. Protocol Violations for this study include, but are not limited to, the following:

- Failure to meet inclusion/exclusion criteria
- Use of a prohibited concomitant medication

Failure of the investigators or study staff to comply with Good Clinical Practice (GCP) guidelines will also result in a protocol violation. The medical monitor will determine if a protocol violation will result in withdrawal of a subject. When a protocol violation occurs, it will be discussed with the investigator and a Protocol Violation Form detailing the violation will be generated. This form will be signed by the Investigator. A copy of the form will be filed in the site's regulatory binder.

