^f Sputum can be collected by spontaneous expectoration. In those subjects unable to spontaneously expectorate, sputum may be induced by inhalation with 3% hypertonic saline using the current TDN SOP

^g CBC with differential, comprehensive chemistry panel, hs-CRP, ESR, direct bilirubin and LDH

^h Calprotectin, MPO, GM-CSF, IL-1 β , IL-6, IL8, IL-17, and TNF- α

ⁱ IL-1 β , IL-6, IL-8, IL-10, IL-17, GM-CSF, MIP-3 α , TNF- α , neutrophil elastase, α ₁-anti-trypsin, and MMP-9

^j RSSQ should be administered if any increased respiratory symptoms

^k Only if Acute Illness/Early Termination Visit is prior to Visit 5

^l MSCs will be derived from bone marrow samples obtained from healthy volunteers and processed and evaluated according to CCC SOP well in advanced of infusion. CF study staff will inform CCC collaborators when hMSCs will be needed approximately 14 days prior to infusion. CCC collaborators will prepare the proper dose to be infused based upon the weight of the subject with CF

^m Infusion is given by slow IV push and takes less than 30 minutes depending upon the volume to be infused

ⁿ Subjects will be monitored in the CRU for 24 hours after the completion of the infusion. Temperature, blood pressure, heart rate, respiratory rate and oxygen-saturation are measured prior to infusion and at 10 (\pm 5), 20 (\pm 5), 30 (\pm 5), 60 (\pm 15), and 90 (\pm 15) minutes and 2 hours (\pm 15 minutes) and 4 (\pm 15 minutes) hours post-infusion and then every 4 (\pm 15 minutes) hours for the remainder of the 24-hour observation period.

^o On Day 2, spirometry should be performed at 24 (\pm 1) hours after completion of infusion

^p An Acute Illness Visit will be arranged for any subject who experiences any abrupt change in baseline clinical status, between Visit 2 and Visit 5

^q An Early Termination Visit will be completed for any subject terminating study participation between Visit 2 and Visit 7.

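### An infused subject who still consents can be taken off study, and beyond one Early Termination Visit nothing continues the scheduled safety measurements

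*Combined protocol and SAP*

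**What the plan says.** Section 12.1 puts stopping treatment and leaving the study under one heading: "The following is a list of possible reasons for study or treatment discontinuation". Adverse event, non-compliance and physician request appear as items separate from withdrawal of consent. Section 13 adds another route: "The medical monitor will determine if a protocol violation will result in withdrawal of a subject". Use of a prohibited medication is one of its two named violations.

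After removal, the plan provides the following:

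- **One further visit.** Section 12.1 says "Subjects will be encouraged to complete an Early Termination Visit". Appendix II footnote q is firmer: "An Early Termination Visit will be completed for any subject terminating study participation between Visit 2 and Visit 7". For a day-of-infusion case, 12.1 adds "If a subject withdraws on the day of hMSC infusion, then the Early Termination Visit will be performed on Day 4-9".
- **Content of that visit (10.15).** It includes RSSQ, vital signs, oximetry, examination, spirometry, urinalysis and safety bloods ("Collect blood for clinical laboratory tests (comprehensive chemistry panel, ESR, hs-CRP" and the rest of the panel). There is no sputum step.
- **Follow-up of an adverse event** "until the abnormal parameter or symptom has resolved or stabilized" (12.1).
- **Survival and new health problems** for 12 months in every infused subject (4.1).
- **Replacement.** "Subjects who withdraw from the study will be replaced if they withdraw before Visit 5" (12.1).

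Section 7 keeps subjects treated for a pulmonary exacerbation in the study and asks that drug changes made because of adverse events be documented. Section 15.1 analyses whatever data are available and leaves a subject out of any analysis for which data are missing.

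**The concern.** In a multi-dose trial, stopping treatment and leaving the study are different events. Here each subject has a single infusion, so after Day 1 there is nothing left to stop. Any of the listed reasons can then only end observation, even in someone willing to keep attending.

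Section 5.1 makes spirometry and RSSQ change up to Visit 7, laboratory change, and sputum culture at Days 7 and 28 part of the primary safety endpoint. If a subject is removed because the infusion went badly, those later measurements are missing for that reason, and the cohort summaries at later visits rest on the subjects who did better.

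One route is easy to picture. Section 9.1.9 leaves treatment of toxicity to the managing physician. Section 7.2 prohibits systemic corticosteroids for an acute problem through Visit 5. Section 13 counts prohibited medication as a violation that may lead to withdrawal. A subject given steroids for an infusion reaction could thus be removed because of the reaction the trial exists to study.

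**Working it through.** The plan has no figure to reproduce on this point. It gives no removal or dropout rate, and the sample size of 15 is justified by feasibility (15.6). The check is a comparison of provisions followed by a count.

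**Do the existing provisions continue the schedule?**

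- The Early Termination Visit is a single occasion and has no sputum step.
- Adverse-event follow-up concerns the abnormal finding only. It may bring some repeat tests but does not carry the visit schedule.
- The 4.1 data can be gathered by telephone and do not include spirometry, laboratory tests, RSSQ or culture.
- The section 7 retention rule covers treated exacerbations only.
- Section 12.1 rules out further evaluations when a subject withdraws and also withdraws consent to disclosure. For a removed subject who has not done so, evaluations are not barred, but none is required.

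None of these continues the scheduled measurements.

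**What one removed subject loses**

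Inputs from Appendix II and section 10: after Day 2, spirometry, safety laboratory tests and RSSQ fall at Visits 3, 4, 5, 6 and 7, which is 5 visit assessments. Post-infusion cultures fall at Days 7 and 28, which is 2. The Early Termination Visit is assumed to take place, and each visit due before removal is assumed to have been done.

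Net loss = scheduled visits missed − 1 Early Termination Visit.

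| Removal | Visits missed | Net loss of 5 | Cultures lost of 2 |
|---|---|---|---|
| Day of infusion | Visits 3–7 = 5 | 5 − 1 = 4 | 2 |
| Day 8 | Visits 4–7 = 4 | 4 − 1 = 3 | 1 (Day 28) |
| Day 22 | Visits 5–7 = 3 | 3 − 1 = 2 | 1 (Day 28) |

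In the first row, the Early Termination Visit (Day 4–9) largely coincides with the Visit 3 window (Day 7 ± 2, so Day 5–9) and can stand in for it, except for the culture. In the other rows, the one visit credited does not fall at the scheduled time of any missed visit.

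**Weight of one removed subject after replacement**

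Cohort sizes from Table 1 (8.3.3) are 3, 3, 3 and 6, total 15. With one removed and one replacement:

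- Cohorts 1–3: 1/(3 + 1) = 25%
- Cohort 4: 1/(6 + 1) = 14%
- Whole study: 1/(15 + 1) = 6%
- If the MTD cohort is pooled with cohort 4 by dose: 1/(3 + 6 + 1) = 10%

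Replacement brings the number of subjects seen at later visits back to plan. It does not bring back the removed subject's measurements, so the loss is in who is represented.

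**The case against.** The case against the point is mainly about its weight.

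- **Removal is discretionary and the route is narrow.** Section 12.1 lists possible reasons under a best-interest standard, section 13 leaves the decision to the medical monitor, and treated exacerbations stay in. This stands, and no rate is available to say how often removal would occur.
- **Section 12.1 can be read as allowing further evaluations** unless consent to disclosure is also withdrawn. That is correct, but permission is not a requirement, and footnote q treats these subjects as ending participation.
- **Much is retained.** Section 4.1 counts every subject who begins an infusion as evaluable. Adverse events and SAEs are captured to Month 12 (9.1.11, 11.2.1). Section 15.3 reports individual data and lists withdrawals with reasons, and the DMC reviews each cohort before the next opens. This limits the harm but does not restore the scheduled measurements.
- **The direction of bias is only partly established.** Removal for non-compliance or an eligibility error need not track tolerability. This stands: the tilt is a risk mainly where removal follows an adverse event or its treatment.
- **The consequence is small for the dose decision.** DLTs are judged over 24 hours, and Month 3 and Month 6 measures drive no escalation. This also stands, although the Day 7 to Day 28 measures fall before the next cohort opens. A missed sputum sample on its own is minor, since 9.1.8 does not treat it as a deviation.
- **The detailed SAP is still to be written** (section 15) and may change how missing data are handled. An analysis plan cannot recover measurements that were never taken.

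**Conclusion.** The concern holds. For an infused, still-consenting subject removed under 12.1 or 13, no provision continues the scheduled spirometry, laboratory tests, RSSQ or sputum culture after one Early Termination Visit. The size is that of the counts above: from 2 to 4 of 5 visit assessments and 1 or 2 of 2 cultures per subject removed before Visit 5, in cohorts where that subject may be a quarter of those infused.

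This assumes that the Early Termination Visit is completed; if it is not, each visit count rises by one. The number of subjects affected is unknown. The likely effect is some tilt in the descriptive later-visit summaries, with little effect on the DLT decision. It should be corrected because the correction is cheap and each subject's course matters in a 15-subject trial. It does not put the dose-escalation design in doubt.

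**What to change.** Amend 12.1, 13 and Appendix II footnote q as follows.

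- **Before infusion:** keep every listed reason for removal.
- **After infusion:** an adverse event, non-compliance, physician request or protocol violation is flagged in the data, and the consenting subject continues the remaining visits and calls, including Day 7 and Day 28 sputum if still due. Only withdrawal of consent, loss to follow-up or death ends follow-up.
- **Safety opt-out:** the investigator or medical monitor may omit any procedure judged unsafe or against the subject's interest. The telephone calls and the 4.1 data to Month 12 are the minimum.
- **Section 13:** for an infused subject, the medical monitor decides whether to flag data or omit procedures.
- **Footnote q:** the Early Termination Visit applies to subjects who end follow-up and agree to attend.

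This takes no position on which rescue treatments should be allowed. The cost is amendment wording and a few visits already in the schedule. The medical monitor gives up the option of ending follow-up in an infused subject. A non-compliant subject may still miss visits, and omitted procedures will still leave gaps, but observation would no longer stop by default.

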13 PROTOCOL VIOLATIONS

A protocol violation occurs when the subject or investigator, fails to adhere to significant protocol requirements affecting the inclusion, exclusion, subject safety and primary endpoint criteria. Protocol Violations for this study include, but are not limited to, the following:

- Failure to meet inclusion/exclusion criteria
- Use of a prohibited concomitant medication

Failure of the investigators or study staff to comply with Good Clinical Practice (GCP) guidelines will also result in a protocol violation. The medical monitor will determine if a protocol violation will result in withdrawal of a subject. When a protocol violation occurs, it will be discussed with the investigator and a Protocol Violation Form detailing the violation will be generated. This form will be signed by the Investigator. A copy of the form will be filed in the site's regulatory binder.

